9 POST-HOC EXPLORATORY ANALYSES

9.1 Sensitivity Analysis of Vaccine Efficacy by Read Count Threshold for Parasite Positivity

We will estimate VE of each RTS,S vs. the control regimen in both the TVC and ATP cohorts using different parasite positivity sequence read count thresholds ranging between 50 and 1000. Point estimates and 95% CIs will be reported to evaluate sensitivity of the VE estimates to the threshold value.

9.2 First New Asymptomatic Infection

It is of interest to assess VE of each RTS,S vaccine regimen to prevent the first new asymptomatic molecularly confirmed infection prior to any clinical malaria. To this end, we define the event of interest as the first new molecularly confirmed infection that does not meet the MAL-094 secondary case definition of clinical malaria (parasitemia > 0 parasites/ μl). The rationale for this event definition is that all molecularly confirmed infections with any *available* evidence of clinical symptoms are disqualified, albeit some symptomatic infections may still be included such as mild symptomatic cases of clinical disease when either the child did not attend a clinic visit or the secondary case definition of clinical malaria was not met (e.g., if the axillary temperature was $< 37.5^\circ\text{C}$).

The occurrence of the secondary case definition of clinical malaria is a competing event in this setting. Therefore, the following analyses might be performed to assess VE of each RTS,S regimen (i.e., comparisons with GP1) in both the TVC and ATP cohorts during primary follow-up:

- (a) the competing risks Cox regression model, and
- (b) the Aalen-Johansen estimation of cumulative incidence.

The output of the analysis in (a) will be a hazard-based VE estimate, with a 95% CI, for each RTS,S regimen and each cohort. The output of the analysis in (b) will be a cumulative incidence curve over time for each of GP1–GP5 and a cumulative VE curve over time for each of GP2–GP5, separately for each cohort.

9.3 Vaccine Effects on Post-infection Outcomes (Analysis of Parasite Density)

Vaccine efficacy against clinical malaria measures a combination of vaccine effects on sterilizing immunity and other effects on post-infection processes such as parasitemia. Since the estimated overall VE against first clinical malaria is greater than the estimated overall VE against first molecular infection, it is of interest to investigate in a post-hoc analysis any vaccine effects on post-infection processes that would elucidate the higher VE against clinical disease. In particular, it is of interest to assess the marginalized mean difference (GP1 minus pooled GP2–5) in parasite density across all new molecularly confirmed infections in the TVC, controlling for baseline covariates that might predict both parasite density and the infection endpoint. Due to “differential cluster sizes” (different numbers of new infections per participant), multiple outputation will be used for valid inference. The analysis will be repeated for the first new molecularly confirmed infection in the TVC, without the need to use multiple outputation. For each of the two endpoints, we will show a histogram of parasite density, separately for GP1 and GP2–5, with zero as a separate category, and report a point estimate of the marginalized mean difference in parasite density with a 95% CI.

Given the finding that selective blockage of 3D7-matched infection acquisition does not explain sieve effects by 3D7 match vs. mismatch on clinical malaria, it is further desirable to evaluate in a post-hoc analysis whether a potential vaccine effect on parasitemia might explain these sieve effects. To this end, we will study whether parasitemia modifies VE against clinical malaria in the ATP cohort by fitting a mark-specific hazard-ratio model (Juraska and Gilbert, 2013) using parasitemia as a quantitative mark. Additionally, we will investigate whether 3D7 match modifies the vaccine effect on parasitemia in the ATP cohort by fitting a linear regression model for the mean parasite density with predictors treatment, indicator of 3D7 match, and an interaction of treatment and 3D7 match.

9.4 Modification of RTS,S Vaccine Efficacy by Baseline Parasite Positivity and Month 2 Force of Infection

Herein, we define baseline parasite positivity as either molecular (≥ 325 read threshold) or microscopic detection of parasite positivity in the sample collected on the day of the first vaccination. We define month 2 force of infection (M2-FOI) as an individual's number of new molecular infections detected *after* the first vaccination visit and no later

than at the month 2 scheduled visit (i.e., M2-FOI measures the number of intercurrent new infections post-first-vaccination by the month 2 visit).

Post-hoc analyses presented in this section aim to address four separate exploratory scientific questions:

1. Did baseline parasite positivity modify VE against the first new molecular infection?
2. Did baseline parasite positivity modify VE against the first new clinical malaria episode?
3. Did M2-FOI modify VE against the subsequent first new molecular infection?
4. Did M2-FOI modify VE against the subsequent first new clinical malaria episode?

We will investigate whether and how each of baseline parasite positivity and M2-FOI variables modified the effect of RTS,S vaccination on (i) the time to the first new molecular infection, and (ii) the time to the first new clinical malaria episode meeting the MAL094 protocol's primary case definition.

Questions 1. and 2. will be addressed in both the TVC and ATP cohorts, while questions 3. and 4. will be addressed in the ATP cohort only, given that M2-FOI is measured at the M2 visit (after randomization).

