Associated with each sample with molecular detection of malaria infection is the complexity of infection (COI), defined as the maximum of (i) the number of unique haplotypes for the CS C-terminus amplicon, and (ii) the number of unique haplotypes for the SERA2 amplicon in the sample. It is expected that the cause of $n = COI > 1$ is multiple distinct malaria infections; thus, COI itself is one estimate of the number of new molecularly confirmed malaria infections that have occurred up to the time of the given sample. However, simultaneous super-infection is possible, and some new malaria infections could be undetected if enough time elapses between infection and sampling, or if antimalarial treatment clears an infection.

The following paragraphs provides more detail on the definition of a new malaria infection.

Malaria infection

A *P. falciparum* infection is defined as amplicon nucleotide sequence-based parasite positive status defined as detection of at least one haplotype supported by at least 50 nucleotide sequence reads and 1% of total reads for at least one of the two amplicons.

New malaria infection

As there is no guarantee of complete clearance of infections, a new infection may originate from a post-enrollment sample that goes from negative to positive, or from a post-enrollment sample that contains a new haplotype that was not previously observed in several previous samples from the same participant. A new infection for the primary objective is defined as at least one of the haplotypes in the post-enrollment sample not being detected in the previous three samples drawn from the same participant regardless of the visit type (scheduled or unscheduled). An exception is made if a haplotype is detected in the first post-enrollment sample not collected on the day of enrollment, in which case it counts as a new infection if the same haplotype was not detected in the single sample from the enrollment visit. Haplotype detection requires observation of at least 50 reads and 1% of total reads supporting the haplotype within a sample. Note that a molecularly confirmed infection in a sample from the enrollment visit does not count as a new infection because the sample was collected prior to administration of the first dose, and therefore the sample should not contribute to measuring the vaccine effect. A molecularly confirmed infection in a sample from an unscheduled visit that occurred on the day of enrollment does not count as a new

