A descriptive sensitivity analysis will be conducted to compare rates of primary endpoint 1, defined in Section 5.1.2, to those of first new infection by either molecular detection or passive detection of secondary-case clinical malaria per the MAL-094 protocol

definition. The descriptive analysis will include tabulating proportions of molecularly detected new infections that are in samples from visits with confirmed secondary-case clinical malaria, and proportions of negative samples for clinical malaria ascertainment that yielded a positive result by the molecular method of detection. Clinical case detection is not included in the primary endpoint definitions under the premise that each infection requires a molecular presentation. Because an infection that was acquired pre-enrollment may first clinically manifest after enrollment, ignoring clinical cases in primary endpoint 1 precludes from erroneously calling a clinical infection the first new infection. Also, ignoring clinical infection events avoids double-counting of infections in primary endpoint 2.

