9.4.2 Inferential Analysis of Potential VE Modifiers of Interest

Cox proportional hazards models, adjusted for baseline covariates, will be used for analysis. Assessments of vaccine effects within the baseline positive subgroup and within the baseline negative subgroup in the TVC or ATP cohort are valid based on randomization. If M2-FOI is uncorrelated or negligibly correlated with treatment assignment in the ATP cohort, assessments of vaccine effects separately within categories of M2-FOI = 0 and M2-FOI > 0 in the ATP cohort are approximately valid based on randomization, and there is minimal risk of post-randomization selection bias induced by subsetting on M2-FOI = 0 vs. M2-FOI > 0. Given that few participants with M2-FOI > 1 had first new malaria infection endpoints, statistical inferences studying M2-FOI analyze M2-FOI as a dichotomous variable $I(M2\text{-FOI} > 0)$, interpreted as whether an intercurrent new malaria infection occurred after the first vaccination and by the third vaccination.

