All models fit to data pooling over both study sites will have a separate baseline hazard function for each site. All models will be fit in parallel for the first new molecular infection endpoint and the first new clinical malaria endpoint.

Cox models will be fit to assess hazard ratio-based VE (RTS,S/control) separately within the baseline positive and baseline negative subgroup, with 95% Wald CIs, and to generate treatment \times baseline positivity two-sided interaction Wald test p-values for the following comparisons:

- **[TVC analyses]** RTS,S regimens GP2–4 pooled (i.e., excluding GP5) vs. the control regimen (GP1) for both combined and individual study sites in the TVC cohort.
- **[ATP analyses]** RTS,S regimens GP2–4 pooled (i.e., excluding GP5) vs. the control regimen (GP1) for both combined and individual study sites in the ATP cohort. GP5 is excluded from the RTS,S pooled group in both the TVC and ATP analyses because the post-dose-3 ATP follow-up period in GP5 is delayed until M7.5–19, whereas, for all other groups including the control group, the follow-up period is M2.5–14. The exclusion of GP5 in the analyses of pooled RTS,S vs. control is of little concern because we hypothesize that neither baseline positivity nor M2-FOI are likely to impact VE during a follow-up period starting 7.5 months after baseline. In addition, GP5 vs. control VE modification analyses in the TVC cohort during the M0–20 period and in the ATP cohort during the M7.5–19 period are evaluated separately as specified in the next bullet.
- Each individual RTS,S regimen (except ATP GP2–3 pooled) vs. the control regimen pooling over the study sites as summarized in the following table:

Analysis Cohort	Study Group and Follow-up Comparison
TVC	GP2 M0-20 vs. GP1 M0-20
	GP3 M0-20 vs. GP1 M0-20
	GP4 M0-20 vs. GP1 M0-20
	GP5 M0-20 vs. GP1 M0-20

ATP	GP2 + GP3 pooled M2.5-14 vs. GP1 M2.5-14
	GP4 M2.5-14 vs. GP1 M2.5-14
	GP5 M7.5-19 vs. GP1 M7.5-19

The ATP cohort analyses will consider the follow-up period from 14 days after the 3rd dose through the scheduled visit at 12 months after the 3rd visit for each of GP1–5.

In addition to the models described above, we will fit model M1-ATP for the GP2–4 vs. GP1 treatment comparison for the follow-up period restricted to 14 days to 4.5 months after the 3rd dose for assessments of VE modification during a period of potentially limited waning of overall VE against the first new infection (or the first clinical malaria).

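### SAP 9.4 does not define what makes a clinical episode new, so illness from pre-existing infection can distort, or hide, modification of VE by baseline positivity

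*SAP*

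**What the plan says.** SAP Section 9.4 studies two modifiers, baseline parasite positivity and infection between first vaccination and the Month 2 visit (M2-FOI). There are two endpoints: the first new molecular infection and "the time to the first new clinical malaria episode meeting the MAL094" protocol's primary case definition. Baseline positivity is "either molecular (≥ 325 read threshold) or microscopic detection of parasite positivity in the sample collected on the day of the first vaccination". On cohorts, "Questions 1. and 2. will be addressed in both the TVC and ATP cohorts"; questions 3 and 4 use the ATP cohort only. Section 9.4.2.1 adds: "All models will be fit in parallel for the first new molecular infection endpoint and the first new clinical malaria endpoint".

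For the molecular endpoint, SAP 5.1.1 defines *new*. A haplotype must be absent from the previous three samples; for the first post-enrollment sample, "it counts as a new infection if the same haplotype was not detected in the single sample from the enrollment visit". Section 9.4 gives no counterpart for a clinical episode: no haplotype link to earlier samples, no washout and no exclusion.

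The SAP knows of the problem. In the closing paragraph of 5.1.3 it keeps clinical cases out of primary endpoint 1 because "an infection that was acquired pre-enrollment may first clinically manifest after enrollment".

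Section 9.4.2 states: "Assessments of vaccine effects within the baseline positive subgroup and within the baseline negative subgroup in the TVC or ATP cohort are valid", on the ground of randomization.

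**The concern.** A baseline-positive child in the TVC analysis carries a known infection at time zero. A later clinical episode may come from those parasites and not from a new bite. Protocol 2.1 says blood-stage merozoites do not express *csp*, so a vaccine that blocks new infection would not be expected to prevent such an episode. Carry-over episodes would then add a similar hazard to both arms and move the positive subgroup's hazard ratio toward 1.

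The treatment-by-positivity interaction is the quantity that Section 9.4 sets out to estimate, so the disturbance acts directly on the result. Questions 1 and 2 could also give different answers partly because one endpoint has a rule for newness and the other has none.

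The safeguards in Section 9.4 do not remove a carry-over episode:

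- The early antimalarial treatment indicator is a covariate, not an event rule. It is absent from model M1-TVC, which adds only age to treatment, positivity and their interaction.
- Matching on Dose 3 date (9.4.2.1.1) and the unmeasured-confounding analysis (9.4.2.3) address confounding, not event definition.
- The 14-day post-treatment exclusion in SAP 7.1 is specified for the primary analyses.
- Starting ATP follow-up 14 days after Dose 3 reduces carry-over but does not exclude it.

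**Working it through.** **Inputs.** Section 9.4 states no effect size or power, so there is no figure to reproduce. Illustrative rates come from Protocol 6.2: 0.50 episodes per year in control and 0.29 on the standard schedule, so HR = 0.29/0.50 = 0.58 and VE = 42%. As a check on these rates, 0.16 vs 0.29 with 250 vs 500 children over one year gives 500(1 − e^−0.29) + 250(1 − e^−0.16) ≈ 163 first events. Schoenfeld power is then 94.7%, consistent with the protocol's claim of at least 90%.

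**Step 1: dilution.** Let f be the share of first clinical episodes in baseline-positive controls that come from the pre-existing infection. Assume no vaccine effect on those episodes and no true modification. Then HR(pos) = f + (1 − f) × 0.58, and the ratio of hazard ratios is HR(pos)/0.58.

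| f (assumed) | HR(pos) | VE in positives | Ratio of HRs |
|---|---|---|---|
| 0 | 0.580 | 42.0% | 1.00 |
| 10% | 0.622 | 37.8% | 1.07 |
| 30% | 0.706 | 29.4% | 1.22 |
| 50% | 0.790 | 21.0% | 1.36 |

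**Step 2: dependence on the window.** The documents do not give f. Suppose a pre-existing infection leads to an episode with probability q = 10–50%, after an exponential delay with mean d = 1–4 months. For a window from t0 to t1 months, f = a/(a + b), where a = q(e^(−t0/d) − e^(−t1/d)) and b = 1 − e^(−0.5(t1−t0)/12).

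| Window | f | Ratio of HRs |
|---|---|---|
| TVC M0–20 | 15–47% | 1.11–1.34 |
| ATP M2.5–14 | 2–40% | 1.02–1.29 |
| ATP M2.5–6.5 (restricted window in 9.4.2.1) | 5–52% | 1.04–1.38 |
| ATP GP5 M7.5–19 | 0–16% | 1.00–1.12 |

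The later ATP start helps over the full window. The restricted window keeps less of the benefit, because it also contains fewer new episodes.

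**Step 3: effect on the interaction test.** Use a normal approximation with SE = √(sum of 1/events over the four cells), two-sided 0.05, and assumed baseline prevalence of 10–20%. The TVC has 300 controls and 900 in GP2–4; for the ATP cohort 250 and 750 are assumed. One cell of the calculation: TVC, prevalence 20%, f = 30%, events 42, 102, 136 and 276. This gives SE = 0.211, log(1.217) = 0.197 and rejection of about 15%.

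| f | TVC rejection | ATP rejection |
|---|---|---|
| 0 | 5% | 5% |
| 10% | 5.6–6.1% | 5.3–5.6% |
| 20% | 7.5–9.5% | 6.4–7.5% |
| 30% | 10.9–15.3% | 8.4–10.9% |

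**Step 4: carry-over in negatives too.** If 5% of control episodes in baseline negatives are also carry-over, HR(neg) = 0.05 + 0.95 × 0.58 = 0.601. The ratios at f = 10, 20 and 30% become 0.622/0.601 = 1.035, 0.664/0.601 = 1.105 and 0.706/0.601 = 1.175.

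**Step 5: masking.** If true VE is 60% in positives and 42% in negatives, the true ratio is 0.40/0.58 = 0.69. At f = 30%, HR(pos) = 0.30 + 0.70 × 0.40 = 0.58 and the observed ratio is 1.00. Real modification has disappeared.

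**The case against.** The strongest reply is that question 2 is about clinical malaria, not about blocked acquisition. Within each baseline subgroup, vaccine against control for any clinical episode is a randomized comparison (in the ATP cohort, subject to selection into the cohort). If already-infected children gain less clinical protection, that is real modification of that estimand. This stands. A reader might infer that the subgroup estimates are invalid, and the documents do not support that. What lacks support is reading them as VE against *new* clinical episodes, which is what the endpoint's name claims.

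Other stronger readings also go too far:

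- *Only positives are affected.* Positivity rests on one day's sample at 325 reads or microscopy. SAP 5.1.1.1 raised the read threshold from 50, and Protocol 2.4.5 says sequestered parasites can go undetected, so some negatives are infected.
- *The molecular endpoint is free of the problem.* Its rule looks back only three samples, so a persistent haplotype missed in three and then seen again counts as new. The difference is one of degree.
- *False modification is created.* That depends on f, which is unknown, and on equal carry-over hazard in both arms. SAP 9.3 leaves open vaccine effects after infection. The bias can equally hide higher VE in positives.
- *Question 4 is affected in the same way.* M2-FOI counts infections detected after the first dose, so equal hazard in both arms is less secure there.
- *No rule exists anywhere.* The case definition sits in the parent protocol, which is not among these documents. The gap can be asserted only for this SAP.

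**Conclusion.** The gap is real and modest. Section 9.4 leaves *new* undefined for clinical episodes, despite the SAP's own recognition in 5.1.3 that pre-enrollment infection can surface later, and none of its adjustments removes such episodes. They are more likely in baseline positives, so the interaction for question 2, and less clearly question 4, can be shifted toward lower VE in positives, or true higher VE there can be masked.

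The concern is greatest for the TVC analysis from Month 0. It is generally smaller in the ATP cohort from Month 2.5, though less so in the restricted window, and small for GP5 from Month 7.5. At VE 42%, carry-over shares of 10 to 50% correspond to ratios of hazard ratios of 1.07 to 1.36. These are illustrations: f, baseline prevalence and persistence are not in the documents, and the calculation assumes no vaccine effect on existing blood-stage infection.

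The analyses are labelled post-hoc exploratory. No primary result changes.

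**What to change.** Keep the all-episode analysis as it is. Making a haplotype-restricted endpoint the main one would change the estimand and is not needed. Add to Section 9.4 a sensitivity analysis of the treatment-by-positivity interaction, in the TVC first and also in the ATP cohort:

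- Count a clinical episode as an event only if its sample carries at least one haplotype not detected in that child's samples before the time origin (first vaccination for the TVC, 14 days after Dose 3 for the ATP cohort). State the read threshold, since 5.1.1 uses 50 and the baseline definition in 9.4 uses 325.
- Censor follow-up at an episode with only previously seen haplotypes.
- Run episodes without usable sequence once as new and once as excluded. A child positive at baseline by microscopy alone has no enrollment haplotypes to compare, so the plan should say how that child's episodes are handled too.
- Report modification of VE against new clinical episodes only where those two versions agree. Describe the all-episode result as modification of VE against any clinical episode.

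The cost is SAP wording and one extra endpoint derivation. Clinical-case samples through Month 20 are already in Tier 1 (SAP 5.2).

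There are two downsides. Some true reinfections with a common haplotype will be removed: Protocol 2.4.3 reports at least four haplotypes per locus at 10% frequency or more at most earlier sites. With both amplicons the loss should be limited, since the simulations in Protocol 2.3 detect an added strain more than 99% of the time over one existing strain and about 95% over five. Some episodes will also lack haplotypes for one or both amplicons; SAP 8.2 expects 20% or more of primary endpoint 1 cases to lack one.

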9.4.1 Descriptive Analysis of Potential VE Modifiers of Interest

All descriptive analysis outputs (summary measures, figures, tables) will be generated for the individual as well as combined study sites. To characterize baseline positivity, the following descriptive outputs will be produced in both the TVC and ATP cohorts:

- prevalence of baseline parasite positivity pooled over GP1–4 and by treatment;
- a scatter/box plot of the date of the first vaccination stratified by baseline parasite positivity status pooled over GP1–4;
- a scatter/box plot of age at enrollment stratified by baseline parasite positivity status pooled over GP1–4.

To characterize M2-FOI, the following descriptive outputs will be produced in the ATP cohort only:

- frequency distribution of M2-FOI by GP2–4 vs. GP1 and by individual treatment arms;
- a bar plot of the percentage of GP1 vs. GP2–4 ATP participants (and of ATP participants by individual treatment arms) for each value of M2-FOI (to assess the association of treatment and M2-FOI);
- a bar plot of the percentage of baseline positive vs. baseline negative ATP participants for each value of M2-FOI, with a participant count on top of each bar (to assess the association of baseline positivity and M2-FOI) pooled over GP1–4;
- a scatter/box plot of the date of the first vaccination stratified by M2-FOI pooled over GP1–4;

- a scatter/box plot of age at enrollment stratified by M2-FOI pooled over GP1–4.

We will summarize correlation in the ATP cohort between baseline positivity and ordered categorical M2-FOI using Spearman's rho. Correlation in the ATP cohort between baseline positivity and the indicator that M2-FOI exceeds zero, $I(M2\text{-FOI} > 0)$, will be assessed using Kendall's tau.

